	
treatment. From then on until the individual patient's end of the trial the investigator must report:
 
 • All AEs/SAEs/AESIs collected by the investigator as instructed in Section 3.3.4.1 for patients who choose Options 1 and 2. • All AEs/SAEs/AESIs the investigator becomes aware of for patients who choose Options 3 and 4 
After the individual patient's end of the trial the Investigator does not need to actively monitor the patient for AEs but should only report relevant SAEs and relevant AESIs of which the Investigator may become aware of by any means of communication, e.g. phone call. Those AEs should be reported on the BI SAE form, but not on the CRF.
 
The rules for Adverse Event Reporting exemptions still apply, please see section 5.3.6.3.

Rationale for change	To align this section with updated standard protocol text.
Section to be changed	6.2.1 Screening Period
Description of change	If the rater at the site concludes that the patient meets diagnostic criteria for APS and has a qualifying NAPLS risk calculator score , both the video-taped interview and the SIPS response forms must be reviewed and diagnosis confirmed by [REDACTED] prior to randomisation. Please refer to the Assessment Procedures Binder SIPS Process Document in the ISF for further information.
Rationale for change	To reflect change to inclusion criteria; clarification on the name of the procedural reference.
Section to be changed	6.2.2 Treatment Period
Description of change	
Please refer to the Assessment Procedures Binder SIPS Process Document in the ISF.
 
Patients experiencing a first episode of psychosis should continue taking study drug at the discretion of the investigator.

Rationale for change	Clarification on the name of the procedural reference; clarification that patients should remain in the study after experiencing psychosis.
Section to be changed	7.1 Statistical Design - Model
Description of change	The primary objective of the statistical analysis is to determine whether BI 409306 significantly reduces the risk of first episode of psychosis increases the likelihood of remission from APS in comparison to placebo. The Cox proportional hazards model, stratified by the NAPLS risk score strata and baseline use of antipsychotic medication, will be used to

	
estimate and test the hazard ratio of BI 409306 vs. placebo.
 
The NAPLS risk score is dichotomized into two strata:
 
• 0.20 ≤ NAPLS risk score < 0.40• NAPLS risk score ≥ 0.40.
Rationale for change	To reflect change in primary endpoint.
Section to be changed	7.2 Null and Alternative Hypotheses
Description of change	Superiority will be declared if the hazard ratio between BI 409306 vs. placebo is significantly less <ins>greater</ins> than 1 at the two-sided type I error level $\alpha = 0.10$.
Rationale for change	To reflect change in primary endpoint.
Section to be changed	7.3.1 Primary Endpoint analyses
Description of change	
The primary endpoint is the time to first episode psychosis remission of from APS as defined in Section 5.1.2.
 
The equality of the hazard rates will be tested by the Wald test for the treatment effect in a stratified Cox proportional hazards model at the two-sided 10% significance level. The model includes the treatment effect and NAPLS risk score as the only covariates and is stratified by NAPLS risk score and baseline use of antipsychotic medication.
 
A hazard ratio of more less than one favors BI 409306.
 
The primary analysis will be performed on the FAS for the full follow-up on treatment period. The date of remission will be the visit date on which the patient taking the assessment meets the remission criteria. The time to remission is defined to be the start of treatment until remission is achieved. Although Ppatients who discontinue study medication will be followed until the end of the trial for the primary endpoint, the data collected after treatment discontinuation will be only used for sensitivity analysis. Patients who are lost-to-follow up will be censored for the primary endpoint at the time of their last known SOPS assessment. Patients who begin taking a new prescription or increase in dose of ongoing antipsychotics will be considered as not eligible for remission. Such patients will be censored at the start of new prescription or increase of dose of ongoing antipsychotics. Further details regarding these analyses will be included in the TSAP.
 
The following sensitivity analyses will be performed: (1) on the primary endpoint that includes only patients from the TS during the time of the on-treatment full follow-up period and (2) excluding patients who were recruited from the enriched

	
population prior to amendment 3 on the portion of the primary endpoint derived from the SOPS (that is, excluding patients with new prescriptions or increases in dose of ongoing antipsychotic medication).

Rationale for change	To reflect change in primary endpoint.
Section to be changed	7.3.2 Secondary endpoint analyses
Description of change	
Time to event endpoints will be analysed using Cox proportional hazard model as described for the primary endpoint analysis. All change from baseline endpoints specified in Section 5.1.2 will be analysed using the restricted maximum likelihood (REML) based mixed effects model with repeated measurements (MMRM). All secondary endpoints specified in Section 5.1.2 will be analyzed using a restricted maximum likelihood estimation based on MMRM for the change from baseline.

Rationale for change	To reflect change in secondary endpoint.
Section to be changed	7.4 Interim Analyses
Description of change	
Once there is a sufficient amount of data collected for review, the DMC will hold meetings three times per year.
 
The number of observed remissions primary endpoints will be compared to the number predicted. If the actual number is lower than predicted (given the actual already documented study time of randomised patients at the scheduled post-baseline SOPS visits; prediction: 35 40% for placebo & 20 57% for BI 409306 at 52 weeks), the sample size may be increased to allow the trial to achieve full power up to a maximum sample size of 400 patients.

Rationale for change	To reflect change in primary endpoint.
Section to be changed	7.5 Handling of Missing Data
Description of change	
All patients who have not converted to psychosis achieved remission will be censored in the analysis of the primary endpoint at the time of last known SOPS assessment.

Rationale for change	To reflect change in primary endpoint.
Section to be changed	7.6 Randomization
Description of change	
The randomisation will be stratified by risk score on the NAPLS risk calculator ($0.20 \leq \text{score} \leq 0.40$ vs. $\text{score} \geq 0.40$), and baseline use of antipsychotic medication.

Rationale for change	To reflect removal of stratification factor.
Section to be changed	7.7 Determination of Sample Size
Description of change	
Remission rate of the population diagnosed with APS and

~~without intervention was assumed to be 40% (Addington, 2011) by 52 weeks. The rate of remission for BI 409306 was assumed to be 57% by 52 weeks. This will lead to a hazard ratio of 1.652 NAPLS has constructed an algorithm to estimate the risk of conversion to first episode psychosis depending on several risk factors. This algorithm, when applied, predicts the conversion rates for patients without treatment, i.e., patients taking placebo. For example, for the group of patients with a risk score ≥ 0.20 , approximately 35% of patients are predicted to convert to psychosis within one year. For the group of patients with risk score ≥ 0.15 , approximately 27% of patients are predicted to convert to psychosis within one year [R16-3564]. Selection of the targeted conversion rate in the APS population is somewhat arbitrary, but the risk score ≥ 0.20 was selected to maximize the risk of conversion to enable the trial to be able to differentiate between treatment and placebo within an acceptable risk/benefit profile.~~

[figure not shown]
Table 7.7: 1 **Power calculations for** sample size (for both arms combined) **of 300** for various **conversion remission** rates for BI 409306 with fixed placebo group aggregate **conversion first remission** rate prediction of **35%40% by 52 weeks**

		BI 409306 group aggregate conversion rate		
		15%	20%	25%
80% power	Total N=115 patients	230	560	
	90% power	160	319	775

Remission Rate for Placebo	Remission Rate for BI 409306	Hazard Ratio	Risk Ratio	Power for N=300	# Events needed in total
40%	52%	1.437	1.300	64.9%	126
40%	55%	1.563	1.375	81.5%	130
40%	57%	1.652	1.425	89.3%	133
40%	59%	1.745	1.475	94.4%	136
40%	61%	1.843	1.525	97.4%	139

Table 7.7: 1 displays the **power achieved for 300 number of total randomized** patients ~~needed to randomise~~ given a group aggregate **conversion first remission** rate of **35-40%** for placebo with two-sided $\alpha= 0.10$ and a user-defined alpha spending boundary at interim analysis of $\alpha=0.01$ (two-sided). Group **conversion remission** rates for BI 409306 treatment of

	
15%, 20%, and 25% 52%, 55%, 57%, 59% and 61% are considered. Sample size considerations for 80% and 90% power are displayed. Total number of events needed to achieve the power reported is also shown.
 
Given conversion remission rates of 35-40% for patients treated with placebo and 2057% for patients treated with BI 409306, the risk ratio is 0.57-1.425 (equating to a 43% risk reduction implying that patients treated with BI 409306 will have 42.5% more chance of achieving remission of APS compared to placebo). and a total sample size of 319 patients is required for 90% power. A sample size of 300 (or 150 per group) was selected as the most logical for establishing proof of concept based on the risk / benefit considerations noted above. In addition this was the sample size used in the previous protocol and is kept the same. This translates to 8889% power. The type I error was selected to be 10% since this is a phase II study meant to provide an understanding of the effectiveness of the drug without being too strict as in a confirmatory setting.
 
Seventy-five One hundred and thirty three (75133) events (conversions-remissions) are needed to be observed to meet the trial objectives. This will not be an event driven trial, so the trial will end when all randomised patients have reached 12 months exposure, regardless of number of conversions remissions observed. However, a blinded sample size assessment will be performed (see Section 7.4) that may allow for an increase in sample size in an attempt to observe the number of conversions remissions necessary for full power.

Rationale for change	To reflect change in primary endpoint.
Section to be changed	9 References
Description of change	The following references were added: R16-0991 R18-0654
Rationale for change	References added in section 1 and 7.
Section to be changed	10.2 Ocular Safety Sub-Study
Description of change	Addition of Ocular safety sub-study
Rationale for change	Section added to provide information on the background, patient selection, design, procedures, endpoints, analytical determination and statistical considerations for the ocular safety sub-study.

APPROVAL / SIGNATURE PAGE

[figure not shown]
Document Number: c08964447

Technical Version Number: 5.0

Document Name: clinical-trial-protocol-version-03

2. LIST OF ABBREVIATIONS

Include a list of all abbreviations used in the TSAP

Term	Definition / description
AE	Adverse Event
APS	Attenuated Psychosis Syndrome
AR(1)	Autoregressive covariance matrix of order 1
BAC App	Tablet based Brief Assessment of Cognition
BACS	Brief Assessment of Cognition in Schizophrenia
BACS SC	Brief Assessment of Cognition in Schizophrenia: Symbol Coding
BCVA	Best Corrected Visual Acuity
BDNF	Brain-derived neurotrophic factor
BI	Boehringer Ingelheim
C-SSRS	Columbia- Suicide Severity Rating Scale
CTP	Clinical Trial Protocol
CTR	Clinical Trial Report
CYP	Cytochrome P450
DRA	Drug Regulatory Affairs
DSM	Diagnostic and Statistical Manual of Mental Disorders
EC	Exclusion Criteria
ECG	Electrocardiogram
EOT	End of Treatment
eCRF	Electronic Case Report Form
FAS	Full Analysis Set
FU	Follow Up
H_0	Null Hypothesis
H_a	Alternative Hypothesis
HR	Hazard Ratio

Term	Definition / description
IC	Inclusion Criteria
ICH	International Conference On Harmonisation
ICF	Informed Consent Form
ICH E9	International Conference on Harmonization of Technical Requirements for Registration of Pharmaceuticals for Human use, E9-Statistical Principles for Clinical Trials
iPD	Important Protocol Deviation
ITT	Intent To Treat
Max	Maximum
Min	Minimum
MMRM	Mixed Model with Repeated Measurements
MedDRA	Medical Dictionary For Regulatory Activities
N	Sample Size
NAPLS	North American Prodromal Longitudinal Study
PANSS	Positive and Negative Syndrome Scale
PK	Pharmacokinetic
PSP	Personal and Social Performance
PT	Preferred Term
RS	Randomized Set
SAE	Serious Adverse Event
SCoRS	Schizophrenia Cognition Rating Scale
SD	Standard Deviation
SOC	System Organ Class
SOPS	Scale of Prodromal Symptoms
TS	Treated Set
TSAP	Trial Statistical Analysis Plan
VAS	Visual Analogue Scale

3. INTRODUCTION

As per ICH E9, the purpose of this document is to provide a more technical and detailed elaboration of the principal features of the analysis described in the protocol, and to include detailed procedures for executing the statistical analysis of the primary and secondary variables and other data.

This TSAP assumes familiarity with the Clinical Trial Protocol (CTP), including Protocol Amendments. In particular, the TSAP is based on the planned analysis specification as written in CTP Section 7 “Statistical Methods and Determination of Sample Size”. Therefore, TSAP readers may consult the CTP for more background information on the study, e.g., on study objectives, study design and population, treatments, definition of measurements and variables, planning of sample size, randomization.

SAS® Version 9.4 or higher will be used for all analyses.

4. CHANGES IN THE PLANNED ANALYSIS OF THE STUDY

Due to recruitment challenges, the trial has a much smaller sample size than originally intended. The following are the changes in the analyses due to the limited sample size:

- No subgroup analyses.
- No evaluation of psychometric properties of SIPS/SOPS.
- No additional sensitivity analyses excluding patients who were recruited from the enriched population prior to amendment 3.

5. ENDPOINTS(S)

5.1 PRIMARY ENDPOINT(S)

The primary endpoint is time to remission from APS within a 52 week timeframe (please see **section 5.1.1** of the CTP).

Per DSM-V, the proposed diagnostic criteria for APS are:

- A. At least one of the following of symptoms is present in attenuated form, with relatively intact reality testing and is of sufficient severity or frequency to warrant clinical attention:
 - Delusions
 - Hallucinations
 - Disorganized speech.
- B. Symptom(s) must have been present at least once per week in the last 1 month
- C. Symptom(s) must have begun or worsened in the past year
- D. Symptom(s) is sufficiently distressing and disabling to the individual to warrant clinical attention
- E. Symptom(s) is not better explained by another mental disorder, including: Depressive or bipolar disorder with psychotic features and is not attributable to physiological effects of a substance or another medical condition
- F. Criteria for any psychotic disorder have never been met.

A diagnosis of APS is defined by the presence of recent attenuated positive symptoms that meet **ALL** of 5 criteria: sufficient **severity** (criterion A), sufficient **frequency** (criterion B), **recency** of onset or worsening (criterion C), associated with sufficient distress or disability to warrant clinical attention (“**warrant attention** criterion,” criterion D), and not likely due to another disorder (“**attribution** criterion,” criterion E).

A patient in remission is defined as someone who no longer meets the severity criterion.

Remission from APS is defined as a score of <3 on all of the P1-P5 Positive Symptom items of the SOPS and maintained until the end of treatment.

5.2 SECONDARY ENDPOINT(S)

5.2.1 Key secondary endpoint(s)

This section is not applicable.

5.2.2 Secondary endpoint(s)

The following are the secondary endpoints as defined in **section 5.1.2** of the CTP.

[figure not shown]
- Time to first episode of psychosis within a 52 week timeframe as adjudicated by the Central Rating Committee.

[figure not shown]
First episode of psychosis defined as:

- One or more SOPS P1- P5 rated a 6
- AND either a symptom is seriously disorganizing or dangerous
- OR one of the symptoms above occurred at least one hour per day at an average frequency of four days/week over the past month
- OR a new prescription or increase in dose of an ongoing antipsychotic medication.

Time of onset of first episode psychosis is defined using the rater's best estimate as determined in the SOPS interview or when the patient began taking a new prescription or increased the dose of antipsychotic medication.

- Change from baseline in everyday functional capacity as measured by Schizophrenia Cognition Rating Scale (SCoRS) total score after 24 and 52 weeks of treatment.
- Change from baseline in the BAC App composite T score after 52 weeks of treatment.
- Change from baseline in Positive and Negative Syndrome Scale (PANSS) positive items score, negative items score, and total score after 52 weeks of treatment.

6. GENERAL ANALYSIS DEFINITIONS

6.1 TREATMENT(S)

As described in **Section 3** of the CTP, patients will be randomized in equal allocation to one of two treatment dosage groups (50 mg and placebo) for analysis purposes.

For randomization purposes 2 arms have been defined:

- BI 409306 50 mg q.d. for 52 weeks.
- Placebo for 52 weeks.

Table 6.1: 1 Treatments and their labels per randomization list

Treatment	Short label
BI 409306 50 mg q.d.	BI 409306 50 mg
Placebo	Placebo

The trial consists of a 28 day screening period, followed by a 52 week treatment period (after randomization), and a 28 day residual effect period for follow-up.

For analysis purposes two periods have been defined in **section 7.3.1** of the CTP:

- Full follow-up
This is the entire study period, beginning with randomization until the end of the follow-up period (or date of last contact), including the residual effect period.
- On-treatment
This includes the time period from treatment start date until drug discontinuation + 7 days.

Patients who discontinue early will be followed up according to the **section 3.3.4.1** of the CTP.

6.2 IMPORTANT PROTOCOL VIOLATIONS

According to latest iPD HTG, important protocol deviations are recorded in the DV template.

6.3 SUBJECT SETS ANALYSED

Screened/Enrolled Set

The screened set includes all patients who were screened for the trial, gave informed consent and had at least one screening procedure at Visit 1.

Randomized Set (RS)

The RS consists of all patients who were screened for the trial and who were randomized to study drug, regardless of whether any study drug was taken.

Treated Set (TS)

The TS includes all patients who were randomized and were documented to have taken at least one dose of study drug.

Full Analysis Set (FAS)

The FAS includes all patients in the TS with at least one baseline and post-baseline measurement of any type. The FAS will be used for the primary and secondary analyses.

The screened set, RS and TS will be used to populate patient disposition and the TS will be used for demographics, baseline characteristics, treatment exposure and safety analyses (including adverse events, laboratory measurements, vital signs and ECG).

Efficacy data will always be analyzed according to the randomized treatment following the intention-to-treat (ITT) principle. If a patient erroneously received a medication kit that included a treatment different from what they were randomized to, the patient's efficacy data will be analyzed according to the treatment they were originally randomized to.

Table 6.3: 1 Subject sets analyzed

Class of endpoint	TS	FAS	Subject set
Primary and key secondary endpoints		X	
(other) Secondary and further endpoints		X	
Safety endpoints	X		
Demographic/baseline endpoints		X	

Analysis periods are defined in the revised CTP and in [section 6.1](#).

6.5 POOLING OF CENTRES

This section is not applicable because country is not included in the statistical model.

6.6 HANDLING OF MISSING DATA AND OUTLIERS

Assessment of remission data (primary endpoint):

All patients will be followed up for remission from APS. As specified in [section 5.1](#), remission from APS has to be maintained until the end of treatment to satisfy the primary endpoint.

Any patient who has not remitted will be censored in the analysis of the primary endpoint at the time of their planned completion of 52-week treatment period or at the time of discontinuation.

Any patient who has remitted but relapsed to APS will be also censored in the analysis of primary endpoint at the time of their planned completion of 52-week treatment period or at the time of discontinuation.

Any patient who has an episode of psychosis will be censored at the time point of psychosis.

Patients who begin taking a new prescription or increase in dose of ongoing antipsychotics will not be considered eligible for remission. Such patients will be censored at the start of new prescription or increase of dose of ongoing antipsychotics.

No missing data will be imputed for primary and secondary analyses.

SCoRS:

For the SCoRS, if an individual item is missing, it should be imputed with the average of the patient's non-missing item scores.

PANSS positive symptoms (secondary analysis)

Change from baseline in PANSS positive symptoms will be evaluated using Mixed effect Model for Repeated Measures (MMRM) approach. This approach allows for missing data, assuming they are missing at random. All patients can be included in the model and missed visits will not be imputed. If a PANSS item is missing, the missing score on that individual PANSS item will not be imputed; if individual PANSS item is missing within a PANSS subscale, this subscale cannot be included in the calculation of the overall PANSS total score. Therefore, patients with missing individual PANSS items will also have a missing PANSS total score at that visit. However, subscale scores will be used for analysis if none of the individual items is missing.

AE dates

Missing or incomplete AE dates are imputed according to BI standards (see "Handling of missing and incomplete AE dates") [\(3\)](#).

6.7 BASELINE, TIME WINDOWS AND CALCULATED VISITS

For all efficacy endpoints, “baseline” is defined as the assessments done at Visit 2, prior to administration of first dose. If this value is not available, the latest measurement before the first time drug administration (at screening (Visit 1), or an unscheduled visit) will be used.

For demographics, medical history, ECG, concomitant antipsychotic medication, AEs, concomitant therapies and vital signs, Visit 1 (screening) will be considered as “baseline”.

Visit will be labelled according to the flow chart in the protocol: Visit 1 (for screening), Visit 2 (randomization and start of treatment), Visits 3-23, End of Treatment (EOT), Follow Up (FU) (28 days after Visit 23 for completed patients; 28 days after EOT for early discontinued patients). Planned and actual test days will be calculated relative to the beginning of study as indicated in the following table.

Table 6.7: 1 Visit calculation relative to study start

Visit	Relative to study start	
	Planned test day (every 14 days)	Actual test day
2	1	1
3	8	Visit 3 date – first dose date +1
4	15	Visit 4 date – first dose date +1
5	22	Visit 5 date – first dose date +1
Etc...
23	365	Visit 23 date – first dose date +1
EOT	Visit 23 + (7 days)	EOT – first dose date + 1
FU	Visit 23 + 28 days	FU date – first dose date + 1

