3.3.1 Main diagnosis for trial entry

Patients meeting the following diagnostic criteria for attenuated psychosis syndrome (APS) as defined in DSM-5 will be included:

- A. At least one of the following of symptoms is present in attenuated form, with relatively intact reality testing and is of sufficient severity or frequency to warrant clinical attention:
 - Delusions
 - Hallucinations
 - Disorganized speech.
- B. Symptom(s) must have been present at least once per week in the last 1 month
- C. Symptom(s) must have begun or worsened in the past year
- D. Symptom(s) is sufficiently distressing and disabling to the individual to warrant clinical attention
- E. Symptom(s) is not better explained by another mental disorder, including: Depressive or bipolar disorder with psychotic features and is not attributable to physiological effects of a substance or another medical condition
- F. Criteria for any psychotic disorder have never been met.

A diagnosis of Attenuated Positive Symptom Syndrome is defined by the presence of recent attenuated positive symptoms that meet ALL of 5 criteria: sufficient severity (criterion A), sufficient frequency (criterion B), recency of onset or worsening (criterion C), associated with sufficient distress or disability to warrant clinical attention (“**warrant attention** criterion,” criterion D), and not have been likely due to another disorder (“**attribution** criterion,” criterion E).

Patients may be enrolled if they are currently taking antipsychotic medication (See [Section 4.2.1](#)). If a patient discontinues an antipsychotic medication, they can be randomized two weeks after discontinuation.

Please refer to [Section 8.3.1](#) (Source Documents) for the documentation requirements pertaining to the in- and exclusion criteria.

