4.1.3 Method of assigning patients to treatment groups

During Visit 2 eligible patients will be randomised to receive BI 409306 50 mg b.i.d. or placebo in a 1:1 ratio according to a randomisation plan. The assignment will occur in a blinded fashion via Interactive Response Technology (IRT).

An IRT will be used to screen and randomise eligible patients, perform subsequent drug assignment, manage initial/re-supply ordering of drug supplies and handle emergency un-blinding. The investigator will receive all necessary instructions to access IRT from the Sponsor or chosen provider. Detailed IRT functions/procedures will be documented in the user requirement specifications (URS) mutually agreed to by the sponsor and the IRT vendor.

Note that the medication number is different from the patient number (the latter is assigned directly after informed consent/assent is obtained). Site personnel will enter the medication number in the eCRF.

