7.3.1 Primary endpoint analyses

The primary endpoint is the time to remission from APS as defined in [Section 5.1.1](#).

The equality of the hazard rates will be tested by the Wald test for the treatment effect in a stratified Cox proportional hazards model at the two-sided 10% significance level. The model includes the treatment effect and NAPLS risk score as covariates and is stratified by baseline use of antipsychotic medication. Breslow's method for handling ties will be used.

The same stratified Cox proportional hazards model will be used to estimate the hazard ratio of BI 409306 vs. placebo and the asymptotic 90% Wald confidence interval. A hazard ratio of more than one favors BI 409306. The analysis will be implemented using █® PROC PHREG. Cox proportional hazard model assumptions will be verified.

[figure not shown]
The primary analysis will be performed on the FAS for the on treatment period. The date of remission will be the visit date on which the patient taking the assessment meets the remission criteria. The time to remission is defined to be the start of treatment until remission is achieved. Although patients who discontinue study medication will be followed until the end of the trial for the primary endpoint, the data collected after treatment discontinuation will only be used for a sensitivity analysis. Patients who are lost-to-follow up will be censored for the primary endpoint at the time of their last known SOPS assessment. Patients who begin taking a new prescription or increase in dose of ongoing antipsychotics will be considered as not eligible for remission. Such patients will be censored at the start of new prescription or increase of dose of ongoing antipsychotics. Further details regarding these analyses will be included in the TSAP.

The following sensitivity analyses will be performed: (1) on the primary endpoint that includes only patients from the TS during the time of the full follow-up period and (2) excluding patients who were recruited from the enriched population prior to amendment 3.

Subgroup analyses are planned and will be pre-specified in the TSAP.

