7.6 RANDOMISATION

Patients will be randomised in blocks to double-blind treatment. Approximately equal numbers of patients will be randomised to each treatment group. The randomisation will be stratified by baseline use of antipsychotic medication. BI will arrange for the randomisation and the packaging and labelling of trial medication. The randomisation list will be generated using a validated system, which involves a pseudo-random number generator so that the resulting treatment will be both reproducible and non-predictable. The block size will be documented in the CTR. Access to the codes will be controlled and documented.

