7.8.2 Laboratory data

The analyses of laboratory data will be descriptive in nature and will be based on BI standards (6). Planned analyses are detailed in **section 7.3.4** of the CTP.

Baseline for safety laboratory parameters will be the last available measurement before the start of randomized treatment. Laboratory measurements taken up to 7 days after the last administration of randomized treatment will be considered as on-treatment.

[figure not shown]
Only patients with at least one available on-treatment value will be included in the analysis of an individual laboratory parameter. All individual data will be presented in listings. If there are multiple safety laboratory values at one visit, the worst of these will be assigned to that visit date measurement.

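### SAP 6.7 takes baseline vital signs from Visit 1 although a pre-dose Visit 2 reading is scheduled, and does not tie the antipsychotic stratum in the analysis to the one used for randomisation

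*SAP*

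**What the plan says.** SAP 6.7 gives two baseline rules. For efficacy endpoints, baseline "is defined as the assessments done at Visit 2, prior to administration of first dose", with the latest earlier pre-dose value as fallback. For a second list the rule is different: "For demographics, medical history, ECG, concomitant antipsychotic medication, AEs, concomitant therapies and vital signs, Visit 1 (screening) will be considered as" baseline. That list includes vital signs and concomitant antipsychotic medication.

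SAP 7.8.2 has a third rule: "Baseline for safety laboratory parameters will be the last available measurement before the start of randomized treatment".

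The protocol uses baseline antipsychotic use in three places:

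- Section 7.6: "The randomisation will be stratified by baseline use of antipsychotic medication".
- Section 7.3.1, on the primary Cox model: "The model includes the treatment effect and NAPLS risk score as covariates and is stratified by baseline use of antipsychotic medication".
- Section 7.3.2, repeated in SAP 7.5.2, enters it as a fixed effect in the MMRM.

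Randomisation takes place at the second visit, not at screening (Protocol 4.1.3): "During Visit 2 eligible patients will be randomised to receive BI 409306 50 mg b.i.d. or placebo in a 1:1 ratio". The Flow Chart places Visit 1 at Day -28 to -7. Protocol 3.3.1 allows antipsychotic status to change in that interval: "If a patient discontinues an antipsychotic medication, they can be randomized two weeks after discontinuation".

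**The concern.** Vital signs: the Flow Chart marks them at both Visit 1 and Visit 2, and its footnote 17 puts the first dose after all baseline assessments. A pre-dose reading on the day of first dose is therefore scheduled, but the SAP uses the older one. Pulse is a parameter of interest, because Protocol 1.2 describes a concentration-dependent increase with this drug. Drift over one to four weeks of screening would enter every change score.

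Antipsychotic use: a stratified test is normally run on the strata used to randomise. If the IRT captures status at Visit 2 and the analysis captures it at Visit 1, some patients could sit in different strata in the two. In the text available, neither document says that the analysis will use the stratum recorded in the IRT. Two programmers could build different strata for the primary model, and each could claim to follow the plan.

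**Working it through.** **1. Vital signs: the rules side by side**

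| Data | SAP baseline | Later scheduled pre-dose value passed over? |
|---|---|---|
| Efficacy | Visit 2 pre-dose (6.7) | No |
| Laboratory | Last value before treatment (7.8.2) | No |
| ECG | Visit 1 (6.7) | No; the extracted Flow Chart shows no Visit 2 ECG |
| Vital signs | Visit 1 (6.7) | Yes, Visit 2 |

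Among these four, only vital signs skip a later scheduled value. Protocol 7.3.4 also lists screening and baseline as separate time points for vital signs.

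The cost can be written down but not evaluated. With equal variance σ² at both times and correlation ρ between them, a change score has variance 2σ²(1 − ρ). If ρ falls as the interval lengthens, an older baseline gives noisier change. The documents give neither σ nor ρ. The expected difference between arms is unaffected, because both arms follow the same rule.

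**2. Antipsychotic stratum: which patients could be discordant**

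- Starting an antipsychotic between Visits 1 and 2 is an exclusion (Protocol 3.3.3, criterion 3). Status can change only from on to off.
- Stopping less than two weeks before randomisation is an exclusion (criterion 4).
- A discordant patient must therefore stop after Visit 1 and at least 14 days before randomisation. With d days between the visits, the stop must fall in the first d − 14 days. That leaves no room when d is 14 or less, and 28 − 14 = 14 days at most.
- The IRT must also record status at Visit 2. If it records status at Visit 1, nobody is discordant.

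**3. How many**

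Expected number = N × (share on an antipsychotic at Visit 1) × (share of those who stop in time). The documents give neither share. On assumed ranges of 10–30% and 2–20%, with the planned N of 300:

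- low: 300 × 0.10 × 0.02 = 0.6
- high: 300 × 0.30 × 0.20 = 18

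This is an illustration, not an estimate. SAP section 4 says the trial is much smaller than planned, so actual counts would be lower.

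**4. Effect on the primary test**

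The plan's own figure first. Protocol 7.7 assumes 40% and 57% remission, 133 events and two-sided alpha 0.10, with stated power 89.3%.

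- HR = ln(1 − 0.57) / ln(1 − 0.40) = 1.652, as stated.
- z = √(133/4) × ln(1.652) − 1.645 = 2.895 − 1.645 = 1.250, giving power 89.4%.
- With the interim look (two-sided 0.01 at 67% information, final critical value 1.651), power is again 89.4%.
- Expected events with 20% exponential dropout: 150 × (0.3619 + 0.5188) = 132.1.

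The design figure reproduces and is not in question.

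The plan's rates were then used in a simulation: 300 patients, 4,000 replicates, a stratified log-rank test at |z| > 1.645 and no interim look. Assumptions not in the documents: 30% on an antipsychotic at Visit 1, remission hazard in users 0.6 times that in non-users, and 5% or 20% of users stopping. Randomisation was balanced within Visit 2 status, which is the case in which a mismatch arises.

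| True HR | Users who stop | Rejection, Visit 2 strata | Rejection, Visit 1 strata |
|---|---|---|---|
| 1 | 5% | 10.8% | 10.9% |
| 1 | 20% | 9.95% | 9.95% |
| 1.652 | 5% | 85.95% | 85.8% |
| 1.652 | 20% | 86.75% | 86.85% |

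The largest difference is 0.15 points. Monte Carlo error on one null rate is √(0.1 × 0.9 / 4000), about 0.5 points, and both analyses use the same simulated data. Power is below 89% in both columns because the assumed slower remission in users reduces events, not because of the choice of stratum.

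**The case against.** The case against has real force.

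- No passage names the visit that defines the IRT stratum. Patients are registered in the IRT at screening (Protocol 6.2.1), and its detailed procedures are in a specification that is not part of these documents. This stands: the mismatch is conditional.
- The SAP 6.7 list is mostly descriptive items, and SAP 7.2 summarises baseline and on-treatment medication. The sentence may govern tables only, with the Cox stratum understood to be the randomisation factor because the protocol words the two alike. This is a fair reading. The stratum would then have no definition in the SAP, and the same clarifying sentence is needed.
- Safety analyses are descriptive with no testing (Protocol 7.3.4). Protocol 1.2 puts the largest pulse effect 20–30 minutes after dosing, with rapid disappearance, and Protocol 5.3.2 does not tie readings to dosing. Timing relative to dose therefore limits detection of the pulse effect more than the age of the baseline does. This stands, and it keeps the vital-sign point small. It does not explain why a scheduled, closer reading should be ignored.

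**Conclusion.** The point holds as a small, cost-free correction. The vital-sign part follows directly from the text: SAP 6.7 uses a reading 7 to 28 days before first dose when a pre-dose reading at Visit 2 is scheduled, contrary to the SAP's own rule for laboratory data. The result is avoidable drift in descriptive change in pulse and blood pressure, of a size that the documents do not allow one to calculate.

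The stratum part is conditional on the IRT using Visit 2 status and on SAP 6.7 governing the model. If both hold, the result is an inconsistency with negligible effect on error rate or power, under the simulation's assumptions.

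A reader might infer more, and the documents do not support it:

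- That the strata will differ. They can differ only under the conditions above.
- That the treatment effect is biased or the test invalid. Visit 1 status is fixed before randomisation, so stratifying on it introduces no bias.
- That a definite number of patients is misplaced. Applying a stopping rate to all 300 planned patients, for example, ignores that only antipsychotic users can stop and that the trial is smaller than planned.
- That safety baselines in general are stale. Of the scheduled safety measurements compared above, this is shown for vital signs only.

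**What to change.** Change SAP 6.7 in two places:

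1. Remove vital signs from the Visit 1 list and define their baseline as the last value before the first dose, normally Visit 2.
2. State that the Cox strata and the MMRM antipsychotic factor use the stratum recorded in the IRT at randomisation. This works whichever visit the IRT used. Visit 1 medication can still be used for descriptive tables if the tables say so.

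Leave the ECG and laboratory baselines as they are. The cost is SAP wording and the matching derivations: the Visit 2 vital signs are already scheduled, and the stratum is needed to randomise. No visit, procedure, sample size or power figure changes.
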